7.0 STUDY MEASUREMENTS AND PROCEDURES

PWD

Baseline Assessments / Observations

1. Chart Review Form

- a. A researcher will conduct a CHART REVIEW to collect the following data:
 - i. Demographics (race/ethnicity, education level, marital status, and number of years living in LTC)
 - ii. Diagnoses
 - iii. Type of dementia
 - iv. Medications

2. Short Portable Mental Status Questionnaire (SPMSQ-T)

- a. A researcher will conduct a direct interview with the PWD to administer the DEMQOL
- b. The Short Portable Mental Status Questionnaire (SPMSQ-T) by Roccaforte et al. (1994) is a brief, validated tool used to screen for cognitive impairment in older adults. It consists of 10 simple questions assessing orientation, memory, and basic arithmetic, providing a quick evaluation of mental functioning in clinical and research settings.

3. Dementia Quality of Life (DEMQOL)

- a. A researcher will conduct a direct interview with the PWD to administer the DEMQOL. However, if the PWD is unable to respond to questions on the DEMQOL, this measure will be administered via proxy interview (with a staff member who is familiar with the PWD).
- b. The DEMQOL is a 28-item self-reported measure related to health-related quality-of-life (HRQL) in residents with dementia. The DEMQOL takes cognition, negative emotion, positive emotion, social relationships, and loneliness into consideration. The DEMQOL-Proxy is a 31-item measure administered to the staff/caregiver and focuses on cognition, negative emotion, positive emotion, daily activities, and appearance.
 - i. Each item on the DEMQOL (and DEMQOL-Proxy) has four response-options:
 - Not at all
 - A Little
 - Quite a Bit
 - A Lot
 - ii. Most items are scored as follows
 - Not at all = 4
 - A Little = 3
 - Quite a Bit = 2
 - A Lot = 1
 - iii. However, since some questions are worded differently, they are reverse coded in the following manner:

Not at all = 1
A Little = 2
Quite a Bit = 3
A Lot = 4

- iv. The total possible score on the DEMQOL ranges from 28 – 112, with lower scores indicating a lower quality of life. The total possible score on the DEMQOL-Proxy ranges from 30 to 120. If a DEMQOL-Proxy is administered, the total score is calculated and scaled to fit the same scoring range as the DEMQOL. If DEMQOL-Proxy total score = X , then $(X/30) \times 28$ = DEMQOL (summary/scaled) total score.

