- v. The final item on the DEMQOL (and DEMQOL-Proxy), asks how the PWD would rate his/her overall quality of life. This item has the following options and coding:
 - Poor = 1
 - Fair = 2
 - Good = 3
 - Very Good = 4
- vi. This final item is not included in the total score on the DEMQOL (nor on the DEMQOL-Proxy)

4. Geriatric Depression Scale – Short Form (GDS-SF)

- a. A researcher will conduct a direct interview with the PWD to administer the GDS-SF.
- b. The Geriatric Depression Scale-Short Form (GDS-SF) is a 15-item screening tool designed to assess depressive symptoms in older adults. It uses a simple yes/no format to evaluate mood, energy, and outlook, making it quick and easy to administer in clinical and community settings.

5. UCLA Loneliness Scale (ULS)

- a. A researcher will conduct a direct interview with the PWD to administer the ULS.
- b. The UCLA Loneliness Scale is a widely used instrument designed to measure subjective feelings of loneliness and social isolation. It consists of 20 items that assess the frequency of loneliness-related thoughts and feelings, providing insight into an individual's perceived social connectedness.

6. Neuropsychiatric Inventory-Nursing Home (NPI-NH)

- a. A researcher will administer the NPI-NH by interviewing a proxy (staff/caregiver) who is familiar with the PWD.
- b. The NPI-NH is a comprehensive assessment of psychopathology in PWD, focused on people residing in nursing homes. The NPI-NH evaluates 12 neuropsychiatric symptoms in dementia patients in the nursing home setting, including the following: Delusions, Hallucinations, Agitation, Depression / Dysphoria, Anxiety, Apathy, Irritability, Euphoria, Disinhibition, Aberrant Motor Behavior, Nighttime Behavior, and Appetite / Eating Changes.
 - i. Each item is initially rated as *present* or *absent*.
 - ii. If the symptom is present, the interviewee is asked to rate the frequency (1 to 4) and severity (1 to 3) of the symptom for the PWD
 - iii. A *frequency x severity* score is then calculated for each item; if a symptom is absent, the frequency x severity score is 0. As such, the total possible

score for each of the twelve symptoms ranges from 0 to 12.

- c. A total score is then calculated across all twelve items
 - i. The total possible score on the NPI-NH ranges from 0 to 144.

7. Baseline Comparison for Engagement

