9.0 VISIT PROCEDURES

PWD

Screening Procedures

A researcher will confirm that the participant meets the following inclusion/exclusion criteria by interviewing a family member or obtaining medical records for the person:

Inclusion: PWD must be at least 65 years old, speak and read conversational English, and be diagnosed with dementia (any type).

Exclusion: PWD will be excluded from the study if they show signs of rapid cognitive decline or physical deterioration over the last six months, as evidenced by medical records.

Baseline Procedures

Chart Review/Interview with Staff

Researchers will collect the following data from each PWD's chart:

- Demographics (race/ethnicity, education level, marital status, and number of years living in LTC)
- All diagnoses
- Type of dementia
- All meds

Baseline Assessment

A researcher will schedule a time to work with the PWD and conduct a direct interview with him/her to administer the SPMSQ, DEMQOL, GDS-SF, and ULS.

Caregiver Interview

Researchers will interview a caregiver to collect data related to neuropsychiatric symptoms (based upon the NPI-NH) and agitation (based upon the CMAI) exhibited by the PWD. In addition, if needed (i.e., if the PWD was unable to respond to the DEMQOL and/or GDS-SF questions), a researcher will interview the caregiver to administer the proxy version of the DEMQOL and/or GDS-SF.

Observations of Standard Activities

For the Phase I study, we will use a large database of participants engaging in activities as the baseline MPES scores. An independent samples t-test will be conducted to examine differences.

Intervention Period Procedures

PWD will be invited to participate in SAFE at Home sessions via videoconference twice per week for two months. The sessions will be led by a Life Enrichment Professional.

Observations of SAFE AT HOME Sessions

Researchers will observe the PWD taking part in SAFE at Home sessions using the MPES. We will aim to conduct multiple observations for each activity type, so that an average score can be calculated for SAFE AT HOME activity programming. Researchers will follow the standard protocols for using the MPES and be extensively trained on how to properly use these measures.

Treatment Fidelity / Process / Satisfaction Measures

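### The DEMQOL item counts and ranges fit no single counting rule, and the paired t-test keeps self-to-proxy pairs after a rescaling that aligns only the score range (minor)

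*Protocol*

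**What the plan says.** **Scoring (Protocol 7.0, item 3).** "The DEMQOL is a 28-item self-reported measure", with a total of 28 to 112. "The DEMQOL-Proxy is a 31-item measure administered to the staff/caregiver", and "The total possible score on the DEMQOL-Proxy ranges from 30 to 120". Items are coded 1 to 4. On the closing overall quality-of-life question: "This final item is not included in the total score on the DEMQOL (nor on the DEMQOL-Proxy"). For conversion: "If a DEMQOL-Proxy is administered, the total score is calculated and scaled to fit the same scoring range as the DEMQOL", using (X/30) × 28.

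**Who answers.** Direct interview is the default. Item 3a adds that "if the PWD is unable to respond to questions on the DEMQOL, this measure will be administered via proxy interview (with a staff member" who knows the participant). Item 3b speaks of staff or caregiver. Section 9.0 names the caregiver, under both the baseline and the post-treatment procedures, and makes the decision separately at each visit.

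**Analysis (SAP).** A paired t-test looks for improvement on DEMQOL. The SAP does not mention version or respondent.

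**GDS-SF.** Section 7.0, item 4 says "A researcher will conduct a direct interview with the PWD to administer the GDS-SF" and gives no proxy route. Section 9.0 allows a proxy "if the PWD was unable to respond to the DEMQOL and/or GDS-SF questions" at baseline, and names a proxy GDS-SF again at post-treatment.

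**The concern.** There are two linked problems. First, the number of scored items sets both the range and the conversion factor, and the counts and ranges in section 7.0 cannot all follow from one way of counting. If the factor is off, every converted proxy score is off by the same percentage.

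Second, a paired test assumes that the two scores in a pair measure the same thing. Rescaling puts the two versions on one range, but it cannot remove a difference between what participants and proxies report. Nor can it remove a difference in content: section 7.0 lists social relationships and loneliness for the self version, and daily activities and appearance for the proxy version. In a self-to-proxy pair, those differences are counted as change in the participant. Two different proxies at the two visits raise the same problem in weaker form.

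A participant who switches to proxy is likely to be one who has lost the ability to answer, so such pairs are not a random subset. With about 12 completers, one pair carries a twelfth of the mean.

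**Working it through.** **1. Ranges.** With k scored items coded 1 to 4, the total runs from k to 4k. Inputs from section 7.0: counts 28 and 31, final item unscored in both.

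| Counting rule | DEMQOL | DEMQOL-Proxy |
|---|---|---|
| Counts include the final item | 28 − 1 = 27, so 27–108 | 31 − 1 = 30, so 30–120 |
| Counts exclude the final item | 28, so 28–112 | 31, so 31–124 |
| Stated | 28–112 | 30–120 |

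Neither rule gives both stated ranges. They agree only if the final item is left out of the count of 28 but included in the count of 31.

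**2. Conversion.** The stated ranges and formula agree with each other: 30 × 28/30 = 28 and 120 × 28/30 = 112. Against the two single rules:

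- 28 and 31 scored: (28/30)/(28/31) = 1.033, or 3.3% too high. Converted scores would run from 31 × 28/30 = 28.9 to 124 × 28/30 = 115.7, above the stated maximum of 112.
- 27 and 30 scored: (28/30)/(27/30) = 1.037, or 3.7% too high.

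A raw proxy total of 90 becomes 84.0 under the stated formula, against 90 × 28/31 = 81.3 or 90 × 27/30 = 81.0. For one self-to-proxy pair in 12 this moves mean change by (84.0 − 81.3)/12 = 0.23 or (84.0 − 81.0)/12 = 0.25 points. In a proxy-proxy pair it only stretches the change by 3.3–3.7%.

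**3. Self-to-proxy pairs.** The documents give no self-proxy gap, SD of change, switch rate, alpha or sidedness. Assumed: gap 5–15 points in either direction, SD of change 8–12, 12 pairs (the expected completers in section 1.0), two-sided alpha 0.05, no true change.

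- Shift in mean change = switches × gap/12. One switch: 5/12 = 0.42 to 15/12 = 1.25. Two in the same direction: 0.83 to 2.50.
- 95% half-width = 2.201 × SD/√12 = 5.08 (SD 8) or 7.62 (SD 12). One switch is therefore between 0.42/7.62 = 5.5% and 1.25/5.08 = 24.6% of the half-width.
- Simulated rejection with normal differences, 400,000 runs per setting (nominal 2.5% per tail):

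| Switches | In the direction of the gap | Against it |
|---|---|---|
| One | 3.1–4.5% | 0.4–1.9% |
| Two, same direction | 4.0–8.1% | 0.04–1.4% |

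With one switch the two tails sum to 4.9–5.0%: the test becomes lopsided without a larger total error.

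**4. Cost of leaving pairs out.** Half-widths for 12, 11 and 10 pairs are 5.08, 5.37 and 5.72 at SD 8, and 7.62, 8.06 and 8.58 at SD 12. That is 5.7% wider with one pair omitted and 12.6% wider with two.

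**The case against.** A reader might infer that the plan has no rule at all for mixed pairs. It does have one, by implication: section 7.0 treats the converted proxy total as the DEMQOL total, and the SAP then runs its paired test on DEMQOL, so the pair is kept. The criticism is of what rescaling can achieve.

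A reader might also infer that the conversion factor is a proven error. The documents do not show that. The ranges and formula agree exactly, and if 28 and 30 items are scored, only an item-count label is loose. The forms that would settle it are not part of these documents.

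Switching may well be uncommon. Sections 5.1 and 5.3 exclude people with signs of rapid cognitive decline over the last six months and require conversational English, spoken and read. Section 6.0 describes people with low cognitive or communication ability as already ineligible for the service, although the section 5 criteria do not repeat this. Intervention lasts eight weeks. One or two switches in 12 is therefore an illustration, not a forecast. The direction of any bias is unknown, and two switches in opposite directions lower both tails, to 0.7–2.4% each.

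The proxy wording differs between sections rather than between visits, since section 9.0 says caregiver at both. Self and proxy measures are kept in the participant binder (15.1), so the version can be recovered. The tracking sheet in 16.0 notes who collected each measure, but that does not show that the forms omit who answered. What stands is that no text requires the same person twice, and that a staff member is an awkward proxy for someone living at home.

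Finally, restricting the main test to same-version pairs is not clearly better. It selects on ability to respond after baseline and may favour improvement.

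**Conclusion.** Minor. The inconsistency between counts and ranges is certain: at least one stated figure is wrong or is counted on a different basis from the others. Its numerical effect is either nil or an excess of 3.3–3.7% in converted proxy scores, depending on the forms.

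Keeping self-to-proxy pairs after rescaling is a real weakness in a test the plan intends to run, but its size rests entirely on assumed gaps, SDs, alpha and switch counts. On those assumptions one switch moves mean change by 0.4–1.25 points and unbalances the tails, with two-sided error near 5%. Section 1.0 expects no change on this distal measure and does not include it in the four success criteria, so the trial's declared success does not depend on it. Confidence is high for the textual points and low for how much bias would occur.

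**What to change.** 1. **Scoring.** Check the number of scored items on the forms in use, correct the counts and ranges in section 7.0, and score each version as mean per scored item × 28. This is identical to the present formula if 28 and 30 are right.
2. **Respondent.** Where possible use the same version and the same proxy person at both visits. Give one proxy definition in 7.0 and 9.0, and record version and respondent.
3. **Analysis.** Prespecify the paired DEMQOL test with all pairs and with same-version, same-proxy pairs only. List each pair that differs in version or proxy, with both scores. State in advance which result is the main one; either choice is defensible.
4. **GDS-SF.** Reconcile section 7.0, item 4 with section 9.0, and apply the same rule if proxy use stays.

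The cost is a few lines of text and one form field, with no added visit or interview. The restricted analysis has an interval about 6% wider for each pair left out of 12.

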During the 8-week intervention period, PWD will participate in SaH sessions through the Social Engagement Portal. Data on engagement and affect will be collected during SAFE at Home sessions using the MPES. In addition, PWD will answer questions related to satisfaction at the end of each session.

Post-Treatment/Distal Measures:

The DEMQOL, GDS-SF, ULS, and NPI-NH will be re-administered at Post-Intervention, allowing us to investigate possible long-term effects. Changes on these longer-term measures are not expected in this Phase 1 study.

[figure not shown]
This App will be considered successful if (1) At least 85% of PWD agree to take part in 80% of the sessions; (2) mean session length is at least 25 minutes; (3) PWD exhibit higher levels of positive engagement/affect and lower levels of negative engagement during SaH sessions, as compared to baseline (based upon the MPES); and (4) PWD report high satisfaction with the app, defined as 85% being satisfied or very satisfied.

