(5) Staff Training Portal (For Engagement Professionals and Engagement Coaches) [Phases 1 and 2] Engagement Professionals will access this portion to take video-based, SCORM-compliant training modules. In order to be eligible to be an Engagement Professional, the person must have experience in recreation therapy, life enrichment, physical therapy, occupational therapy, speech therapy, or a related field. The person must have at least one year of experience working with PWD. So, we expect our engagement professionals to have most of the basic qualifications needed to work effectively with PWD. That being said, our training will be designed to ensure that the person has the appropriate knowledge and skills to facilitate a videoconference-based session with PWD. More specifically, there will be five main training modules. (1) Video Conferencing Best Practices, (2) Overview of the 10 SaH Activities, (3) Communicating with PWD, (4) Tips for Facilitating Activities with PWD via Videoconference, and (5) Using the SaH Website and App. After completing the self-study online training courses and taking a test that shows that he/she has acquired the necessary knowledge to implement SaH sessions, each Engagement Professional will schedule a Mock Session with an Engagement Coach. The Mock Session will be scheduled within the Staff Training Portal. During the Mock Session, the Engagement Professional will connect with two Engagement Coaches, who will participate in a simulated SaH session, which will be led by the trainee. If the Engagement Professional shows competence at facilitating the mock session (based upon a 20-item checklist of key processes for leading SaH), he/she will become a certified SaH Engagement Professional. He/she will then be able to facilitate sessions as they are needed. Engagement Coaches will also have access to this portion of the app, so they can check progress trainees have made on the self-study online courses, review test results, and also start the Mock Sessions. Please note that Engagement Coaches will be trained initially by taking the Online Training courses and then doing the Mock Session (like Engagement Professionals). However, in addition, in order to become a certified Engagement Coach, the person will need to facilitate 30 SaH sessions (receiving good reviews from Members), pass a knowledge test, and receive further individualized training.

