PWD will participate in SAFE at Home for two months during the Intervention Period of the Study. A variety of data will be collected during and/or after the session.

1. Ease of Use and Satisfaction Measure

After each session, the PWDs will be asked simple questions related to ease of use and

satisfaction (e.g., Did you find the activity easy to use? Did you enjoy the activity? Would you recommend it to others?)

2. Observations of PWD in SAFE AT HOME Sessions w/ MPES

- a. Researchers will observe PWD's engagement and affect during SAFE AT HOME sessions using the MPES (Camp, Skrajner, & Gorzelle, 2015). The MPES is described above. There are six different types of activities, and each activity type will be used at least six times by each SAFE AT HOME group. Each participant will be observed multiple times during the intervention period, so that averages can be calculated for each type of engagement/affect.

Post-Treatment Assessments

The following measures will be collected again at post-treatment:

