Researchers will complete a Session Observation / Evaluation Form for each scheduled session, even if the session does not actually occur due to the PWD's unavailability or refusal to participate. Data collected on the Session Observation / Evaluation Form is detailed above.

Post-Treatment Procedures

Post-Treatment Assessment

A researcher will schedule a time to work with the PWD and conduct a direct interview with him/her to administer the DEMQOL, GDS-SF, and ULS.

Caregiver Interview

Researchers will interview a caregiver to collect data related to neuropsychiatric symptoms (based upon the NPI-NH) and agitation (based upon the CMAI) exhibited by PWD. In addition, if needed (i.e., if the PWD was unable to respond to the DEMQOL and/or questions), a researcher will interview the caregiver to administer the proxy version of the DEMQOL and/or GDS-SF.

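### Can six activity types each be used at least six times per group when the stated schedule gives 16 sessions?

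*Protocol*

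**What the plan says.** The minimum for activity content is in Protocol section 7.0, under the MPES observations made during sessions: "There are six different types of activities, and each activity type will be used at least six times by each SAFE AT HOME group".

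The schedule is stated in three places. Section 1.0 says: "During the 8-week intervention period, PWD will participate in SaH sessions through the Social Engagement Portal". Section 9.0 says: "PWD will be invited to participate in SAFE at Home sessions via videoconference twice per week for two months". Section 7.0 gives the length again: "PWD will participate in SAFE at Home for two months during the Intervention Period of the Study".

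No section states the total number of uses, the total number of sessions, or how many activity types one session holds. Section 6.0 describes how a session is run in the Social Engagement Portal, but without a count. The SAP has no session or activity count either. It asks for multiple observations of each participant, averages them within participant, and compares those means with known means by a one-sample t-test.

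**The concern.** A reader who multiplies the figures gets two numbers that do not match: 36 uses promised against 16 sessions scheduled. If a session is built around a single activity type, the promise is missed by more than half. Two types in every session still falls short.

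Three other details seem to add to the doubt. The example satisfaction questions in section 7.0 speak of the activity in the singular. Section 9.0 allows for sessions that fail to happen: "Researchers will complete a Session Observation / Evaluation Form for each scheduled session, even if the session does not actually occur". The staff training list in section 6.0 includes a module titled "Overview of the 10 SaH Activities", and the protocol does not say how ten activities relate to six types.

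If the mismatch were real, each group could receive less of each activity type than the protocol promises, and the number of observations behind each participant's MPES mean might be in doubt. The first success criterion, "At least 85% of PWD agree to take part in 80% of the sessions", might also seem to rest on an unclear number of sessions.

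**Working it through.** The documents give no total to reproduce, so the check builds both totals from the stated inputs.

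**Inputs**
- Activity types: 6; minimum uses of each type per group: 6 (Protocol section 7.0).
- Sessions per week: 2 (section 9.0).
- Length: 8 weeks (section 1.0), also given as two months (sections 7.0 and 9.0).
- Types per session: not stated.
- Assumption: each group meets on the twice-weekly schedule stated for participants. No separate group schedule is given.

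**Totals**
- Minimum uses per group = types x uses per type = 6 x 6 = 36.
- Sessions = sessions per week x weeks = 2 x 8 = 16. If two months is stretched to nine weeks, 2 x 9 = 18.

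**Uses delivered, by types per session**

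| Types per session | 16 sessions | 18 sessions |
|---|---|---|
| 1 | 16 uses (16/6 = 2.67 per type) | 18 uses (18/6 = 3.0 per type) |
| 2 | 32 uses (32/6 = 5.33 per type) | 36 uses (6.0 per type) |
| 3 | 48 uses (48/6 = 8.0 per type) | 54 uses (54/6 = 9.0 per type) |

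**Average needed to reach 36**
- 36/16 = 2.25 types per session, or 36/18 = 2.0.
- One mix that works over 16 sessions: 12 sessions of two types and 4 of three, since 12 x 2 + 4 x 3 = 36.

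The two statements are therefore compatible at 2.25 or more types per session over 16 sessions, and incompatible below that. The documents do not say which case applies.

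**Does anything in the analysis use 36?**
- MPES: the SAP asks for multiple observations per participant, and Protocol section 7.0 likewise sets no number. Section 9.0 aims for several observations of each type, but only to form one average for the whole programme. No analysis by activity type is planned.
- Attendance: the criterion is a percentage of sessions. With 16 sessions the cut is 0.8 x 16 = 12.8, so 13 sessions, whatever the number of types in each.
- Session length and satisfaction: neither criterion refers to activity types.
- Sample size: the 12 expected completers do not depend on it.

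**The case for a change.** The strongest case for a change is that six uses per type is the only minimum the protocol sets for content delivered to a group, and two of the simplest readings of an 8-week schedule miss it. A reader has to supply a session design to make the figures agree. At one type per session, an even spread of 16 sessions gives four types three uses and two types two uses (4 x 3 + 2 x 2 = 16). A participant who attends 13 of 16 sessions, enough for the 80% cut, could miss all the uses of one type. The remedy would also be cheap, because it is wording only.

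The arithmetic stands, and so does the observation that the number of types per session is not given. The inference to a conflict does not, for these reasons:

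- The singular wording about the activity is in an example question, and it could refer to the session as a whole. Elsewhere section 6.0 speaks of activities in the plural when describing what the session leader has to hand. Neither passage settles the number.
- The provision for sessions that do not occur is worded for the unavailability or refusal of the individual participant. A group session can go ahead without one member, so this does not show that group-level uses are lost.
- Activities and activity types are different units. Ten activities can fall into six types, so the training module title shows no inconsistency.
- Dividing "mean session length is at least 25 minutes" by the number of types gives 25/2.25 = 11.1 minutes per type. But 25 minutes is a success threshold for the mean, not a planned length, so this does not rule out several types per session.
- The number of sessions follows from the stated 8 weeks at two per week. The 80% criterion therefore has a usable denominator of 16.
- Whether each type was used six times can be counted directly from what was delivered, whatever the number per session.

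The participant who misses one type is a possible case under one reading, but it would not affect the planned comparison. That comparison averages over all of a participant's observations and does not require every type to be represented.

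**Conclusion.** The concern correctly identifies a missing detail but does not establish an error. At least 36 uses and 16 sessions agree if sessions average 2.25 or more activity types. They disagree at one type per session (16 uses) or two (32 uses). The protocol does not say which applies, and nothing in it excludes the first.

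This rests on the assumption that groups meet on the schedule stated for participants, and on reading the intervention as 8 weeks. Nine weeks would lower the required average to 2.0 and would not change the conclusion.

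The gap is one that the study team fills when it plans session content, and this review takes no position on which schedule or content is right. On the statistical side there is nothing to gain. The MPES comparison, the attendance, session-length and satisfaction criteria, and the sample size all stay the same whether or not the number of types per session is written down. No change to the plan follows.
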